Immediate. Based upon prior RCT outside of the United States, the use of silicone ureteral stents has the potential to decrease pain and LUTS after URS.(12) Decreased pain and LUTS after URS secondarily could decrease the rate of ambulatory healthcare utilization, opioid prescriptions, postoperative ED visits, and unplanned hospitalizations. It could also decrease the number of days required to miss work due to recovery.

Long-range. Decreased pain and LUTS after URS secondarily could decrease a patient's exposure to opioid analgesia postoperatively. Less patient requirements for opioid analgesia could decrease the incidence of new persistent long-term use of opiates in these patients.

Section 5: STUDY OBJECTIVES**Section 5.1: Primary Objectives**

1. To determine the health-related quality of life and symptoms in patients with urinary stone disease stented with silicone or polyurethane stents at ureteroscopy.

Section 5.2: Secondary Objectives

1. To compare 30-day emergency department visits and hospitalization rates between study arms
2. To compare rates and intensity of ambulatory healthcare encounters after ureteroscopy and stenting between study arms
3. To compare stone-free rates between study arms
4. To compare abnormal imaging findings after ureteroscopy and stenting between study arms

Section 5.3: Exploratory Objectives

1. To compare days taken off work by patient between study arms
2. To compare days taken off work by caregiver between study arms
3. To compare Ecological Momentary Assessments (EMA) measured via daily text message for 10 days between study arms
4. To compare Composite score difference between Winratio and Desirability Of Outcome Ranking (DOOR) between study arms
5. To compare number of patients receiving opioid prescriptions between study arms
6. To compare ICIQ-s score at 7 days between study arms
7. To compare ICIQ-s score at 4 weeks between study arms

Section 5.4: Endpoints

- Primary Efficacy Endpoint(s):
 - Silicone stent placement will be associated with significantly improved PROMIS® scores of pain intensity and interference at 7 days compared to non-silicone stent placement.
- Secondary Efficacy Endpoint(s):
 - Silicone stent placement will be associated with equivalent PROMIS® scores of pain intensity and interference at 4 weeks compared to non-silicone stent placement.

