A clinically meaningful change in pain PROMIS® score is between 4 and 6 and the standard deviation of the score is 10(16-18). Assuming a 5 t-score PROMIS® pain point difference between 2 arms and a standard deviation of 10, a t-test including 101 patients per arm has 90% power with a 2-sided alpha = 0.025. Assuming a 10% loss-to-follow-up, accrual of 224 study treated patients (112 patients per arm) is planned. Our planned analysis does not match this calculation because we will adjust for the baseline pain to ensure any imbalance prior to surgery is accounted for. However, this power calculation, by ignoring the adjustment of baseline pain, is accurate if the correlation of baseline pain with our outcome is 0. If the correlation is greater than 0, then we will have more power than described.(19)

Section 11.3: Populations for Analyses

Modified Intent-to-Treat (m-ITT) Population: All participants eligible and randomized who complete the pain intensity and pain interference questionnaire between 7-10 days post-URS will be included.

Subjects will be analyzed by assigned treatment at randomization. This is the main population for efficacy analyses.

Per-Protocol Population: All Patients eligible and randomized patients who complete the pain intensity and pain interference questionnaire between at 7 days post-URS will be included per treatment arm received. This second population will be used to assess the robustness of the primary and secondary efficacy outcomes.

Safety Population: All patients who are randomized and receive a stent will be define the safety population and used for all safety analyses. Subjects will be analyzed by assigned treatment arm.

Section 11.4: Statistical Analyses

General Approach

Descriptive statistics for the study population will be reported using frequentist statistics. In general, continuous measures will be reported using means and standard deviations or medians and the interquartile range as the distribution warrants. Categorical variables will be reported as counts and proportions.

Analysis of the Primary Efficacy Endpoints

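### Read literally, Section 11.3 drops patients from secondary endpoints because of a day 7-10 pain survey that those endpoints do not need

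*Combined protocol and SAP*

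**What the plan says.** Section 11.3 sets out three populations.

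- **Modified intent-to-treat (m-ITT):** "All participants eligible and randomized who complete the pain intensity and pain interference questionnaire between 7-10 days post-URS will be included". Patients are analysed as randomized, and the section adds: "This is the main population for efficacy analyses".
- **Per-protocol:** also restricted to people who answered the pain "questionnaire between at 7 days post-URS will be included per treatment arm received". Its purpose is stated as: "This second population will be used to assess the robustness of the primary and secondary efficacy outcomes".
- **Safety:** "All patients who are randomized and receive a stent will be define the safety population". It is used for safety analyses, by assigned arm.

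Section 5.4 lists as secondary efficacy endpoints PROMIS pain at 4 weeks, LURN SI-10 at 7 days and 4 weeks, the 30-day utilization composite, abnormal imaging within 60 days and stone-free rate within 60 days. Section 11.4 names the m-ITT set for the primary ANCOVA only. For the secondary endpoints it gives models and tests but no population.

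The data sources are separate. Sections 8.1 and 8.3 have the post-operative course entered in the registry at 60 days. The footnotes to the Section 9 table give the week-4 survey its own window, days 22 to 42.

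**The concern.** Completing the day 7-10 survey happens after randomization and may depend on how the patient is doing. The primary endpoint cannot be observed without that survey, but the registry and week-4 endpoints can. If the general rule in Section 11.3 governs them, known outcomes are set aside for want of an unrelated questionnaire. The per-protocol analysis does not bring those patients back, because it has the same type of filter.

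Two things are at stake. One is precision. The other is the accuracy of the utilization results: a patient in hospital or the emergency department around days 7 to 10 may be less likely to answer, and emergency visits and hospitalizations are the first secondary objective in Section 5.2. Such a patient could appear as a serious adverse event in the safety set yet be missing from the utilization composite.

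**Working it through.** **Inputs from the documents.** Section 11.2: difference 5, SD 10, two-sided alpha 0.025, 90% power, 101 per arm, and "Assuming a 10% loss-to-follow-up, accrual of 224 study treated patients (112 patients per arm) is planned".

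**Plan's own figure.** A noncentral t calculation gives power 0.898 at 100 per arm and 0.901 at 101, so 101 reproduces. Inflation: 101/0.9 = 112.2 per arm and 202/0.9 = 224.4, which the plan takes as 112 and 224.

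**Number left out.** 224 - 202 = 22. This carries over the 10% planning allowance, which is not a forecast of survey non-completion. At 5% the number is 11, at 15% 34, at 20% 45.

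**Case 1: non-completion unrelated to outcome.**
- Standard error ratio: sqrt(112/101) = 1.053, about 5% larger.
- 4-week PROMIS, 95% half-width for the difference, no baseline adjustment: 1.96 x 10 x sqrt(2/n) = 2.62 points at n = 112 and 2.76 at n = 101.
- Stone-free rate, assumed 60% in both arms: 1.96 x sqrt(2 x 0.6 x 0.4/n) = 12.8 percentage points vs 13.5. If 70% are imaged (assumed), 15.3 vs 16.1. Missed imaging costs more than the filter.

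**Win ratio under assumed rates.** The documents give no event rates. Assumed non-silicone arm: 55% no contact, 22% phone or message, 11% clinic, 7% emergency department, 4% hospital, 1% ICU. The silicone arm is shifted by a common odds ratio of 2, and no utilization ranks best. Win ratio = P(silicone level lower)/P(silicone level higher) = 0.366/0.197 = 1.86. Power is from 100,000 simulated trials per scenario with a tie-corrected rank-sum test at two-sided 5%.

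| Set analysed | Win ratio | Power |
|---|---|---|
| All stented, 112 per arm | 1.86 | about 72% |
| Completers, loss unrelated to outcome, 101 per arm | 1.86 | about 68% |
| Completers, 60% response after an emergency visit or worse, 93% otherwise | 1.85 | about 64% |

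If half of the non-completers have usable registry data, the fix gives about 70% instead of 68%, or 69% instead of 64%. If none do, it gains nothing. At an odds ratio of 1.6, power is 42% unfiltered against 36-39% filtered.

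**Case 2: response depends on events, equally in both arms (60%/93%, assumed).** Take the proportion with an emergency visit or worse.
- Non-silicone, true 7 + 4 + 1 = 12.0%. Among completers: 0.120 x 0.60/(0.120 x 0.60 + 0.880 x 0.93) = 0.0720/0.8904 = 8.1%.
- Silicone, true: odds (0.12/0.88)/2 = 0.0682, so 6.4%. Among completers: 0.0638 x 0.60/(0.0638 x 0.60 + 0.9362 x 0.93) = 0.0383/0.9089 = 4.2%.
- Difference: 5.6 points becomes 3.9.

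A harsher example assumes true rates of 10% vs 20%, with 40% of event patients missing the survey in both arms and 10% missing overall. The mean difference falls from 10.0 to 6.7 points and power from 57% to 35%.

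**Case 3: response after an event differs by arm (60% vs 80%, assumed).** The win ratio becomes 1.73 or 1.98 instead of 1.86, depending on which arm responds less. With no true effect it is 0.92 or 1.08 instead of 1.00, and type I error is 6.2%.

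**The case against.** **The filter on secondary endpoints is inferred.** Section 11.3 calls the m-ITT set the main population, not the only one. Section 11.4 attaches it by name only to the primary ANCOVA, and its reference back for 4-week PROMIS is to the models. An analysis of all available data is therefore a possible reading. This stands as far as it goes: Section 11.4 contains no explicit exclusion. But the looser reading is not written, and the general rule in Section 11.3 is.

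**Other analyses catch some of these patients.** Section 11.4 tests each utilization component under exploratory analyses, and qualifying hospitalizations enter the safety set as serious adverse events. The cover is partial: the exploratory tests also state no population, and safety reporting does not capture emergency visits, clinic visits or calls as such. Neither returns anyone to the secondary analyses.

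**The cost is small and rests on assumed rates.** True for precision. Section 8.9 also allows unreachable participants to be withdrawn, and Section 8.3 accepts that some patients miss imaging, so some non-completers may have no later data at all.

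**Readings that go too far.** A reader might infer that the utilization comparison is seriously invalid. One scenario with equal true rates of 15% gives a false difference of 5.0 points and 19% type I error, but it needs 10% of event patients to miss the survey in one arm and 40% in the other. Nothing in the documents supports such a gap. Patient blinding (Section 10.4) and the reminders, day 8-9 contact and phone or paper completion (Section 8.1) make it less likely. A reader might also take 22 as a ceiling, which a planning allowance cannot be. In the other direction, a reader might infer that equal response in both arms removes bias; that holds approximately for the win ratio, not for event rates or their difference.

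**Conclusion.** The point holds as a cheap improvement. The only general rule for efficacy analyses ties the secondary endpoints to a post-randomization survey that the registry and week-4 outcomes do not require, and no other set is named for them. The primary analysis is unaffected.

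The size depends on why surveys are missed. Loss unrelated to outcome costs modest precision. Loss related to events understates emergency and hospitalization rates and their difference, even with equal response by arm, and leaves the win ratio almost unchanged. Only response that differs by arm would move the win ratio materially, and the design makes that less likely. Only the SD of 10 and the 10% loss come from the documents. Event rates, response rates, the imaged share and the odds ratios are assumptions, so the figures show a range and are not predictions.

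**What to change.** - State in Sections 11.3 and 11.4 that utilization, abnormal imaging and stone-free rate are analysed by assigned arm in all eligible randomized patients who receive a stent, whether or not the day-7 survey was completed. This is close to the existing safety set and matches the treated patients whom Section 7 counts toward 224.
- Analyse the imaging endpoints among those imaged, and report by arm the numbers not imaged and the numbers without registry data. This does not solve missing imaging, but it makes it visible.
- Analyse 4-week PROMIS in everyone with a week-4 survey, and let the LURN mixed model use every available score.
- Report day-7 survey completion by arm and by event status.
- Keep the completer ANCOVA as the primary analysis.

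The cost is a few sentences and slightly more programming, with no new data collection. The downside is that denominators will differ across endpoints and must be shown in each table.

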The primary endpoints of the study are PROMIS® pain intensity and PROMIS® pain interference t-scores. Each endpoint will be analyzed separately using an ANCOVA model for each. Using the MITT population for analysis, the t-score of the PROMIS® outcome at 7 days post-URS will be the dependent variable and treatment arm and pre-treatment (baseline) PROMIS t-score will be independent variables. The primary comparison of interest is treatment arm. The baseline adjusted mean pain score at 7-days will be reported by arm with the 97.5% confidence interval and a type-3 F-test will test the hypothesis that pain differs between the two treatment groups. Each endpoint modeled will test the effect of treatment arm adjusting for baseline with a type I error of 2.5% for an overall study type I error of 5%.

An analysis in the per-protocol population will be assess the robustness of the effect found in the primary analysis. Additionally, a multivariable model will be considered to account for other patient or surgical variables that may be unbalanced between the arms including timing of stent removal or stone location.

Analysis of the Secondary Endpoints

Additional health-related quality of life endpoints including PROMIS® Pain scores at 4 weeks will be analyzed with similar models described for the primary endpoint. A linear mixed model will be used to compare LURN SI-10 scores at 7 days and 4 weeks between treatment arms. Each analysis will report means with 95% confidence intervals at each time for each arm with a model based type-3 F-test comparing treatment arms.

Healthcare utilization within 30 days of URS will be assessed using a composite endpoint. The composite healthcare utilization metric within 30 days will be a composed score based upon utilization by the patient with each patient assigned a score based upon the highest utilization level that they participate in with levels defined in decreasing order:

5. Hospitalization and ICU care
4. Unplanned hospitalization
3. Emergency department visit
2. Ambulatory encounter: Clinic visit
1. Ambulatory encounter: Phone call or message

We will compare the composite score ranking between the treatment arms using a WinRatio analysis using the unmatched approach.(20) The median composite score for each arm will be reported, along with the WinRatio and associated 95% confidence interval and p-value.

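### The main efficacy set asks for both pain scales although each is tested in its own model, so a valid score on one scale may be dropped

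*Combined protocol and SAP*

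**What the plan says.** Section 11.3 (Populations for Analyses) admits to the m-ITT set those eligible and randomized participants "who complete the pain intensity and pain interference questionnaire between 7-10 days post-URS will be included". It adds: "This is the main population for efficacy analyses". The per-protocol set in the same section carries the same joint condition on the two scales.

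Section 11.4 (Analysis of the Primary Efficacy Endpoints) names PROMIS pain intensity and PROMIS pain interference as the two primary endpoints and says: "Each endpoint will be analyzed separately using an ANCOVA model for each". The set for both is fixed by "Using the MITT population for analysis". Each model takes the 7-day score of one scale as outcome, with treatment arm and a baseline PROMIS score as covariates, and is tested at 2.5%. Section 11.1 likewise states two separate null hypotheses.

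Figure 1 prints the two scales as one block of nine items: items 1-3 for intensity and items 4-9 for interference. The plan does not say when a scale, or the form, counts as complete. It gives no missing-data rule for the primary endpoints; the only mention of missing data in Section 11.4 concerns the exploratory daily text-message models.

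**The concern.** The entry rule and the analysis do not match. Entry is decided jointly on two scales, but each model needs the 7-day result of only one. A patient who answers items 1-3 and stops has a full set of intensity answers. On the ordinary reading of the rule that patient is outside the m-ITT set and so outside the intensity model. The same holds in reverse for a patient with interference answers only. The per-protocol analysis does not bring such patients back, and no imputation rule does either.

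At stake is primary outcome data that have already been collected, and hence some precision on each endpoint. Using every observed outcome under the assigned arm is also closer to the intention-to-treat principle that the set's name invokes.

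**Working it through.** **Inputs from Section 11.2:** a difference of 5 T-score points, SD 10 ("the standard deviation of the score is 10"), two-sided alpha 0.025 per endpoint, 101 evaluable patients per arm, 10% loss to follow-up, 224 treated patients in total.

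**Input not in the documents:** the share p of responders with exactly one usable scale. I assume p = 2%, 5% and 10% to show a range.

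**Formula.** For n per arm, power is the probability that a noncentral t variable with 2n - 2 degrees of freedom and noncentrality (5/10) x sqrt(n/2) exceeds the two-sided 0.025 critical value in absolute size.

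**Step 1: the plan's own figure.** Section 11.2 states that "a t-test including 101 patients per arm has 90% power with a 2-sided alpha = 0.025". Solving for 90% power gives n = 100.56, so 101 per arm. At n = 101 the noncentrality is 0.5 x sqrt(50.5) = 3.55 and power is 90.1%. With 10% loss, 224 x 0.9 = 201.6, or about 202 responders. The stated design reproduces, and this point does not dispute it.

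**Step 2: the joint rule.** If a share p of the 202 responders has only one scale, both models run on 101 x (1 - p) per arm.

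**Step 3: per-scale sets.** If the one-scale patients split evenly, each model regains half of them and runs on 101 x (1 - p/2) per arm. If all of them complete the same scale, the model for that scale regains all of them (101 per arm, 90.1%) and the other model gains nothing.

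| p (assumed) | One-scale patients of 202 | Joint rule: n per arm, power | Per-scale, even split: n per arm, power | Gain, even split | Gain, all on one scale |
|---|---|---|---|---|---|
| 2% | about 4 | 99.0, 89.5% | 100.0, 89.8% | 0.3 points | 0.6 points |
| 5% | about 10 | 96.0, 88.5% | 98.5, 89.3% | 0.9 points | 1.7 points |
| 10% | about 20 | 90.9, 86.6% | 96.0, 88.5% | 1.9 points | 3.6 points |

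Gains are taken before rounding the powers. The last column is an upper bound and applies to one of the two models only.

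**Step 4: a different base for the share.** Suppose instead that 10% of the 112 treated per arm have neither scale and a further 5% or 10% have exactly one. The joint rule then leaves 112 x 0.85 = 95.2 or 112 x 0.80 = 89.6 per arm, with power 88.2% or 86.0%. Per-scale sets with an even split leave 98.0 or 95.2, with power 89.2% or 88.2%. The gains are again about 1 and 2 points.

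**Step 5: the baseline covariate.** Section 11.2 sets the correlation with baseline to zero and notes that power is higher otherwise. Replacing the SD by 10 x sqrt(1 - r^2), a 10% loss from 101 per arm leaves power of about 90% at an assumed r = 0.3 and about 92% at r = 0.4. The table is therefore on the conservative side.

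**The case against.** The strongest reply is that the rule may never bite. Section 11.3 refers to a single questionnaire, and Figure 1 shows one short block. If completing it means returning the form, a patient who skips some interference items stays in the set and contributes an intensity score. Section 8.1 also provides reminders, contact on days 8 and 9, and REDCap, phone or paper as alternatives, so one-scale responders should be few. This stands as far as it goes: a reader might infer that such patients are certain to be lost, and the text does not establish that. But it does not remove the point. Completion is left undefined, the ordinary reading requires both parts, and nothing says that items are mandatory.

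A second reply is that one common set serves the interim rule in Sections 10.5 and 11.4, which requires both worse intensity and worse interference. That is a reason for tidiness rather than a need: the rule can combine two adjusted differences that were estimated separately.

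A reader might also infer bias, on the view that patients who recover badly skip the items on errands, recreation and socializing and so vanish from the intensity model. The documents give no data on which items are skipped, by whom, or in which arm. This remains a conjecture, and I do not rely on it.

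**Conclusion.** The point holds as a mismatch of definition with a probably small effect. Read as written, Section 11.3 may drop a valid score on one scale because the other is missing, and neither primary model needs that restriction. With an even split, the power recovered per scale is below 1 point unless partial completion exceeds about 5% of responders, and about 1.9 points at 10%.

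A reader might take the full falls from 90.1% (to 89.5%, 88.5% or 86.6%) as the expected cost on both endpoints. They are not: a per-scale set recovers that much only if every one-scale patient completed the same scale, and then for that scale alone.

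The figures rest on assumed completion shares, the plan's difference of 5 and SD of 10, and zero correlation with baseline. They do not call the 101 per arm or the total of 224 into question. This is a desirable clarification, not a threat to the trial's conclusions.

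**What to change.** In Section 11.3, define the m-ITT set per endpoint: for each pain scale, all eligible randomized patients with a scorable day 7-10 result on that scale, analysed by assigned arm. State when a scale with skipped items counts as scorable. The per-protocol definition repeats the joint condition and should be aligned in the same way. Settle the wording before outcomes by arm are examined.

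The cost is a sentence or two. Everyone admitted under the joint rule stays in; each model can only gain patients. The small downside is that the two primary models, and the two estimates used in the interim rule, may rest on slightly different numbers, which should be reported. No new data and no change in sample size are needed.

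The change leaves one wider matter as it is: the set would still depend on a response given after randomization.

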It is not anticipated that either arm will be associated with adverse events above and beyond what is experienced normally with these therapies. No more than minimal increased risk to the participants is expected for the present study. All potential participants are planning to undergo a surgical procedure (URS) with a board-certified urologist trained in URS with stent placement in accordance with AUA guidelines. They will be placing either a non-silicone (standard) ureteral stent or a silicone ureteral stent, both of which are FDA approved. All of which is considered usual care.

At the end of ureteroscopic procedure, a ureteral stent will be placed by the urologist in the standard fashion that each urologist is trained to perform. Stent sizing, technique, duration and removal technique will be determined by the individual urologist and their standard practice.

Patients randomized to the silicone stent cohort will utilize the Coloplast Imajin Hydro (Silicone Hydro-Coated Double Loop Ureteral Stent)

- This stent is commercially available and is being used in accordance with approved labeling: "The Silicone Hydro-Coated Double Loop Ureteral Stents are used for:
 - Drainage of the upper urinary tract over fistulas or ureteral obstacles
 - Healing of the ureter"
- Stent sizes
 - 6fr x 24

-
- 6fr x 26
 - 6fr x 28

Patients randomized to the non-silicone stent cohort will utilize any commercially available non-silicone ureteral stent for its approved indication. The stents denoted below are commonly used non-silicone stents and are not individually compared against the object of the study (Imajin Hydro silicone stent above).

- Device model(s)
 - Boston Scientific
 - Percuflex™
 - HYDROGEL COATED Percuflex Plus™
 - Contour™
 - Becton Dickinson (Bard)
 - Bard double pigtail soft polyurethane
 - Cook
 - Sof-Flex double loop polyurethane
- Stent size(s)
 - 6fr x 24
 - 6fr x 26
 - 6fr x 28

Specific assessments obtained on the operative day, include:

- Ureteral stent characteristics
 - The ureteral stents in the comparative effectiveness study are FDA approved commercially available devices that will be utilized by the urologists. Urologists will be trained and educated on documenting the specific size, brand and name of the ureteral stent used in the operative report. This data will be collected through the ROCKS clinical registry.

Section 8.3: Post-Operative

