Adverse event (AE) monitoring and reporting is a routine part of every clinical trial and is done to ensure the safety of subjects enrolled in the studies as well as those who will enroll in future studies using similar agents. Data on adverse events will be collected from the time of the initial study intervention through 30 days after the study intervention. Any serious adverse event that occurs more than 30 days, and before 60 days of the study intervention and is considered related to the study intervention must also be reported. Serious Adverse Events (SAEs) will continue to be followed until:

- Resolution or the symptoms or signs that constitute the serious adverse event return to baseline;
- There is a satisfactory explanation other than the study intervention for the changes observed; or
- Death.

The investigator is responsible for the detection, documentation, grading, and assignment of attribution and expectedness of events meeting the criteria and definition of an AE or SAE. The definitions of AEs and SAEs are given below. It is the responsibility of the principal investigator to ensure that all staff involved in the trial is familiar with the content of this section.

Any medical condition or laboratory abnormality with an onset date before the initial study intervention will be considered pre-existing in nature. Any known pre-existing conditions that are ongoing at the time of study entry should be considered medical history.

For this study, non-serious AEs will not be reported to the IRB. SAEs will be reported in keeping with the governing IRBs guidelines.

Section 10.2: Definitions

1. Adverse Event

For the purposes of this trial, an adverse event (AE) is considered any untoward medical occurrence in a patient receiving study treatment that has or potentially has a causal relationship with this treatment. Any untoward medical occurrences that are unrelated to the study intervention will not be considered adverse events.

Symptoms of kidney stone disease and expected side effects from ureteroscopy lithotripsy and stent placement are not considered adverse events for this study. The following symptoms are indicative of underlying kidney stone disease and expected side effects from ureteroscopy with laser lithotripsy and stent placement, and will not be reported as adverse events (unless the event meets the criteria of an SAE):

- Hematuria
- Irritative voiding symptoms (e.g., urinary frequency, urgency, dysuria)

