- Abdominal/flank/bladder pain
- Nausea and/or vomiting
- Dizziness and lightheadedness
- Urinary retention

Abnormal laboratory values or test results constitute adverse events only if they induce clinical signs or symptoms or require therapy. They are to be captured under the signs, symptoms, or diagnoses associated with them.

2. Serious Adverse Event

An adverse event is considered “serious” if, in the view of the investigator, it results in any of the following outcomes:

- Death
 - If death results from (progression of) the disease, the disease should be reported as an event (SAE) itself.
- A life-threatening adverse event

- An adverse event is considered 'life-threatening' if, in the view of either the investigator [or sponsor], its occurrence places the patient or subject at immediate risk of death. It does not include an adverse event that, had it occurred in a more severe form, might have caused death.
- Inpatient hospitalization or prolongation of existing hospitalization for > 24 hours.
- A persistent or significant incapacity or substantial disruption of the ability to conduct normal life functions
- A congenital anomaly/birth defect
- Important medical event
 - Any event that may not result in death, be life-threatening, or require hospitalization may be considered serious when, based upon appropriate medical judgment, they may jeopardize the patient and may require medical or surgical intervention to prevent one of the outcomes listed in this definition of "Serious Adverse Event". Examples of such medical events include allergic bronchospasm requiring intensive treatment in an emergency room or at home; convulsions that do not result in inpatient hospitalization or the development of drug dependency or drug abuse.

Hospital visits for conditions not associated with the urinary stone will not be collected or reported as SAEs.

3. Expected Adverse Event

An adverse event (AE) is considered "expected" if it meets the criteria of an AE per section 10.2, and is a known risk of general anesthesia and ureteroscopy such as:

- Myocardial infarction, deep vein thrombosis, cerebrovascular accident, pulmonary embolism, fever, UTI, sepsis, perinephric hematoma, acute kidney injury, ureteral injury or perforation, ureteral stricture or scarring, stent migration or dislodgement, stent encrustation

4. Unexpected Adverse Event

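### Safety is grouped by assigned arm only, so a stent-specific event in a patient who received the other stent type is counted under a device that patient did not have

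*Combined protocol and SAP*

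**What the plan says.** Section 11.3 defines three populations, each with its own grouping rule.

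- **Safety.** "All patients who are randomized and receive a stent will be define the safety population and used for all safety analyses". The next sentence gives the grouping: "Subjects will be analyzed by assigned treatment arm".
- **Modified intent-to-treat (main efficacy set).** "Subjects will be analyzed by assigned treatment at randomization".
- **Per-protocol.** Patients with the 7-day pain questionnaires "will be included per treatment arm received". Its purpose is stated: "This second population will be used to assess the robustness of the primary and secondary efficacy outcomes".

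Three other places bear on the point. Section 10.2 defines an adverse event as "any untoward medical occurrence in a patient receiving study treatment that has or potentially has a causal relationship with this treatment". Its list of expected events includes "stent migration or dislodgement, stent encrustation". Section 8.2 has urologists trained in "documenting the specific size, brand and name of the ureteral stent used in the operative report", with these data collected through the ROCKS clinical registry.

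**The concern.** Whether a stent migrates or encrusts depends on the stent in the ureter, not on the one allocated. The safety population admits any randomised patient who received a stent of either type, and its grouping rule uses the allocation. A patient allocated silicone who receives polyurethane is in the silicone column, and so is any event caused by the polyurethane stent.

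For efficacy, grouping by allocation protects the randomised comparison. For harms it has a cost: crossover pulls the two columns together, which makes a device-related excess harder to see. The plan allows for assigned and received stents to differ, since it groups the per-protocol set by arm received. That set cannot serve for safety, because it is confined to patients with the 7-day questionnaires and is reserved for the robustness of efficacy results.

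**Working it through.** **1. Does the text allow misplacement?** Set side by side:

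| Population | Entry | Grouping | Use |
|---|---|---|---|
| m-ITT | eligible, randomised, pain questionnaires at days 7–10 | assigned | main efficacy |
| Per-protocol | eligible, randomised, pain questionnaires at 7 days | received | robustness of efficacy |
| Safety | randomised, received a stent | assigned | all safety analyses |

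No row combines the safety entry rule with grouping by stent received, and Section 11.4 adds none. Section 7 counts toward the 224 only patients who receive the study treatment, and Section 8.9 allows replacement of randomised patients who do not. Both rules govern accrual. Neither removes a randomised, stented patient from the safety population.

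**2. The denominator.** The only plan figure used below is 112 per arm (Section 11.2). The underlying calculation reproduces. For a 5-point difference, SD 10, two-sided alpha 0.025 and 90% power, the exact t-test needs 100.56 per arm, rounded up to 101, and power at 101 is 0.901. Adding 10% gives 101 × 1.10 = 111.1, rounded up to 112 per arm, or 224 in total. The present point does not affect the sample size.

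**3. Size, by assumption only.** The documents give no rate of receiving the non-assigned stent and no adverse event rates. Let pS and pN be the true event rates with silicone and non-silicone stents, and c the proportion receiving the other type.

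- One-way crossover out of silicone: the silicone arm shows (1 − c)·pS + c·pN and the other arm shows pN, so the apparent difference is (1 − c)(pS − pN).
- Crossover at rate c in both arms: the apparent difference is (1 − 2c)(pS − pN).

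With pS = 10% and pN = 5%, one-way:

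- c = 5%: 0.95 × 10% + 0.05 × 5% = 9.75% against 5%.
- c = 10%: 0.90 × 10% + 0.10 × 5% = 9.5% against 5%.

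The range over c, with a second assumed pair of rates:

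| c | Patients per 112 | 10% vs 5%, one-way | 10% vs 5%, both arms | 5% vs 2%, one-way | 5% vs 2%, both arms |
|---|---|---|---|---|---|
| 0 | 0 | 5.0 | 5.0 | 3.0 | 3.0 |
| 2% | 2.2 | 4.9 | 4.8 | 2.94 | 2.88 |
| 5% | 5.6 | 4.75 | 4.5 | 2.85 | 2.70 |
| 10% | 11.2 | 4.5 | 4.0 | 2.70 | 2.40 |

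The last four columns are apparent differences in percentage points. The formulas depend only on pS − pN, so the same shrinkage applies if silicone has the lower rate.

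**4. Against sampling error.** At 112 per arm the standard error of a 10% vs 5% difference is √[(0.10 × 0.90 + 0.05 × 0.95)/112] = √(0.1375/112) ≈ 3.5 points. The one-way loss of 0.25 to 0.5 points is about 1/14 to 1/7 of that. In events, the expected number in patients who crossed over is 112 × 0.05 × 0.05 = 0.28 at 5% crossover and 112 × 0.10 × 0.05 = 0.56 at 10%.

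**The case against.** There is a good case for leaving the rule alone. The trial is a pragmatic comparative effectiveness study. Comparing harms by assigned arm keeps the randomised comparison and matches the main efficacy set. If surgeons change stent type because of what they find at operation, a comparison by stent received is confounded by the difficulty of the case. Section 11.4 describes no adverse event table or between-arm safety test, so no stated comparison is being diluted. Individual serious events are attributed by the investigator (Section 10.1) and the actual stent is on record, so a single event can be traced to its device whatever column it sits in. Most of the expected events in Section 10.2, such as myocardial infarction or pulmonary embolism, have no evident link to stent material.

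Much of this stands. A reader might infer that the plan contradicts itself, because relatedness is judged against treatment received while grouping follows assignment. The documents do not support that: no section requires safety to be grouped by stent received, and assigned-arm grouping is a defensible choice. The confounding argument also stands, and is a reason to keep the assigned-arm summary.

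What remains is narrower. The grouping rule covers all safety analyses, so it would govern any safety summary that is produced. Tracing single events does not correct a summary by arm. Keeping the randomised comparison does not require it to be the only one.

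**Conclusion.** The point holds as a cheap improvement. As written, a stent-specific event in a patient who received the non-assigned type would be summarised under a device that patient did not have, and a difference between devices would be understated.

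A reader might go further and infer that a safety signal is likely to be hidden. The documents do not support this. They give no crossover or event rates, and Section 8.2 does not anticipate adverse events in either arm beyond those normally seen with these therapies. The dilution under the assumed rates is a small fraction of the sampling error and vanishes if every patient receives the assigned type. The reading of the text is firm; the practical impact is unknown and probably modest.

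**What to change.** In the Safety Population paragraph of Section 11.3, replace the grouping sentence with wording such as: *Safety summaries will be grouped by the type of stent actually placed (silicone or non-silicone), taken from the brand and name recorded at operation. The same summaries by assigned arm will be given as supportive. Patients whose placed stent type differs from the assigned type will be counted and listed.*

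The cost is one extra set of tables and a short listing. No new data are needed, and the sample size and efficacy analyses do not change. The drawback is possible confounding of the as-received comparison if stents are switched because of operative findings. The assigned-arm summary guards against this, and the listing shows how many patients are involved. The change should be made before the data are analysed, so that the grouping is not chosen after events are known.
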